# 8.2.9 Prior and Concomitant Medications

Appropriately qualified and trained medical personnel will use this form to collect information about prescription and over-the-counter medications used by participants. At screening, the form will be used to record medications taken by the participant in the 2-week period prior to screening. At weekly, end-of-medication/treatment, and follow-up visits the form will document medications taken since the previous data collection visit.

# 8.2.10 Adverse Events (AEs) and Serious Adverse Events (SAEs)

Appropriately qualified and trained medical personnel will assess for any medical or psychiatric side effects, by asking: "How have you been feeling since your last visit?" AEs will be recorded at each visit after consent according to the adverse event reporting definitions and procedures outlined in the protocol. If a reported AE suggests medical or psychological deterioration, it will be brought to the attention of the study medical clinician for further evaluation. SAEs will be medically managed, reported, and followed in accordance with applicable regulatory requirements.

# 8.3 Drug Use Measures and Psychological Measures

# 8.3.1 Timeline Follow-back (TLFB)

The Timeline Follow-back procedure (Sobell & Sobell, 1992; Fals-Stewart, 2000) will be used to elicit the participant's self-reported use of alcohol and illicit substances before and during the entire study period. At screening, this form will be used to assess substance use reported by the participant for the 30-day period prior to screening. The TLFB will be administered at each study visit throughout the active treatment phase and through the end of the follow up period to document the participant's self-reported use of substances for each day since the previous TLFB assessment.

# 8.3.2 Urine Drug Screen (UDS)

Urine drug screens will be collected at every clinic visit, in most cases, before assessing selfreported drug use or dispensing medications. All urine specimens will be collected using FDAapproved one-step temperature-controlled urine drug test cups following all of the manufacturer's recommended procedures. The UDS will test for the presence of the following drugs: opiates, oxycodone, barbiturates, benzodiazepines, cocaine, amphetamines, methamphetamines, marijuana, methadone, and Ecstasy (MDMA). A further validity check will be performed using a commercially available adulterant test strip that indicates normal ranges for creatinine, pH (at minimum), nitrate, glutaraldehyde, specific gravity, bleach and pyridinium chloromate in human urine. In the event urine specimen tampering is suspected, study staff should request a second sample and may observe the urine collection process according to clinic standard operating procedures.

# 8.3.3 Visual Analog Craving Scale (VAS)

Participants' craving for opioids and cocaine will be documented on a visual analog scale (VAS) that ranges from 0 (no craving) to 100 (most intense craving possible). This scale will be completed at screening and once weekly throughout the active treatment phase, at the end-of-medication visit (if medication is stopped early), at the end-of-treatment visit (last visit of Week 8), and at each follow-up.

# 8.3.4 The Beck Depression Inventory (BDI)

The Beck Depression Inventory (Beck & Steer, 1993) will be used to assess symptoms of depression. A participant who scores in the range for possible depression (score of 15 or higher) or reports possible suicidal ideation will be assessed by a qualified clinician before leaving the clinic. This self-administered assessment will be completed at screening and once weekly throughout the active treatment phase, at the end-of-medication visit (if medication is stopped early), at the end-of-treatment visit (last visit of Week 8), and at each follow-up.

# 8.3.5 Treatment Effect Assessment (TEA)

The TEA (Ling, 2009) is a 4-item self-administered assessment that uses a Likert scale (1-10) to document changes in four life domains: substance use, personal responsibilities, health, and citizenship. Analyses are underway addressing psychometric properties of this measure. The TEA will be collected at screening, at week 5, at the end-of-medication visit (if medication is stopped early), at the end-of-treatment visit (last visit of Week 8), and at each follow-up.

# 8.3.6 World Health Organization Quality of Life BREF (WHOQOL-BREF)

The WHOQOL-BREF (The WHOQOL Group, 2004) instrument comprises 26 items, which measure domains of physical health, psychological health, social relationships, and environment. The WHOQOL-BREF is a shortened version of the original instrument that may be more convenient for use in large research studies or clinical trials. It assesses the individual's perceptions in the context of their culture and value systems, and their personal goals, standards and concerns. The WHOQOL instruments were developed collaboratively in a number of centers worldwide, and have been widely field-tested. The WHOQOL-BREF will be self-administered at screening, at the end-of-medication visit (if medication is stopped early), at the end-of-treatment visit (last visit of Week 8), and at the 3-month follow up.

# 8.3.7 PRISM Suicide and Homicide Screening

The PRISM Suicide and Homicide Screening form is a structured, reliable interview modified from the Psychiatric Research Interview for Substance and Mental Disorders- PRISM (Hasin, et al. 1996). The form will be used as a periodic assessment of suicide and homicide risk

throughout the study. Participants who represent a significant suicidal/homidal risk must be assessed by a qualified clinician before leaving the clinic. The PRISM Suicide and Homicide Screening Assessment will be collected at screening, at week 5, at the end-of-medication visit (if medication is stopped early), and at the end-of-treatment visit (last visit of Week 8).

# 8.3.8 Opioid Use Questionnaire

An abbreviated version of the Opioid Use Questionnaire will distinguish the main type of opioid used by the participant, whether a prescription opioid or heroin. Also assessed will be the onset of the use, the participant's perception of the substance that is most problematic, and their present treatment goal. This questionnaire will be self-administered at screening.

#### 8.3.9 DSM-IV-TR Checklist

The DSM-IV-TR Checklist is a semi-structured interviewer administered instrument that provides current diagnoses for substance use disorders based on DSM-IV diagnostic criteria. The DSM-IV Checklist will be completed at screening to determine eligibility.

#### 8.3.10 Risk Assessment Battery (RAB)

The Risk Assessment Battery (RAB) (Navaline et al., 1994) is a self-administered assessment of engagement in activities that increase the likelihood of contracting HIV. Several scores that measure drug risk, sex risk, and total risk will be computed. This measure will be completed at screening, at the end-of-medication visit (if medication is stopped early), and at the end-of-treatment visit (last visit of Week 8).

#### 8.3.11 Self-Help Assessment

The Self-Help Assessment includes items to assess previous self-help participation. This measure was adapted from the Alcoholics Anonymous Involvement Scale (AAIS; Tonigan et al., 1996). This self-administered assessment will be completed at screening, at the end-of-medication visit (if medication is stopped early), at the end-of-treatment visit (last visit of Week 8), and at each follow-up.

#### 8.3.12 Addiction Severity Index Lite (ASI-Lite)

The ASI-Lite is derived from the Fifth Edition of the ASI (McLellan et al., 1992), a structured clinical interview that yields scores for seven areas of functioning typically impacted by addiction, including medical status, employment status, drug use, alcohol use, family status, legal status, and psychiatric status. The ASI-Lite will be completed at screening, at the end-of-medication visit (if medication is stopped early), at the end-of-treatment visit (last visit of Week 8), and at each follow-up.

#### 8.3.13 Fagerström Test for Nicotine Dependence

The Fagerström Test for Nicotine Dependence (FTND) is used for assessing nicotine dependence (Fagerström and Schneider, 1989; Heatherton et al., 1991) and will be self-administered at screening, at the end-of-medication visit (if medication is stopped early), and at the end-of-treatment visit (last visit of Week 8).

#### 8.4 Compliance Measures

#### 8.4.1 Dose Logs (DL)

These forms will document amount of medication administered in-clinic, dispensed for takehome dosing, and reported as taken by the participant. Medications to be recorded on these forms include naloxone, oral naltrexone, XR-NTX, and BUP (or PLB). These forms will be completed at relevant clinic visits through the end of the active treatment phase.

#### 8.4.2 CBT Attendance Log

A CBT attendance log will be completed to document attendance or non-attendance at each weekly CBT session during the active treatment phase.

# 9.0 TRAINING

The study staff will be trained and certified as specified in the study Training Plan. Training will cover standard NIDA training for all CTN trials (e.g., Good Clinical Practices), as well as protocol-specific training as needed (e.g., assessments, study interventions, fidelity to the protocol and safety procedures, data management and collection, research procedures including understanding reliability and validity, and problem solving). Support mechanisms are identified (e.g., who to contact for aid, questions, resources). All study staff will also be required to complete any local training requirements per their study sites and IRBs. Further details are presented in the study Training Plan.

# 10.0 STATISTICAL ANALYSES

# 10.1 General Design

#### **10.1.1** Study Hypothesis

The primary hypothesis is that buprenorphine, administered in the presence of naltrexone, can reduce the number of cocaine use days occurring over the 30-day evaluation period (days 25-54).

#### **10.1.2** Primary Endpoint

The primary endpoint is the number of cocaine use days during the 30-day evaluation period. The evaluation period will be the last 30 days of the active medication period and will end on the day prior to initiation of the taper. Under the protocol schedule this would be days 25 to 54 inclusive. Cocaine use will be measured by self-report, corroborated with thrice-weekly urine drug screens. Scores for individuals who initiate the evaluation period will be included, and those who discontinue participation will have their score at the time of withdrawal scaled to the 30-day evaluation period.

#### **10.2** Rationale for Sample Size and Statistical Power

The study has been designed to include 300 individuals randomly assigned at a 1:1:1 ratio to the 3 treatment arms. The sample size was developed from a simulation study of the anticipated trial characteristics considering the number of abuse days, withdrawal probabilities, probability of underreporting abuse and effect size. Prior studies of a similar population (NIDA CTN-0007 Motivational Incentives for Enhanced Drug Abuse Recovery: Methadone Clinics) indicates that in a thirty day period, participants had about 9 cocaine abuse days, with a standard deviation nearly the size of the mean (mean=9.5, sd=8.5). The endpoint of this study is the number of cocaine use days during the 30 day evaluation period. Absent a treatment effect, it is assumed that each individual's daily use follows a Bernoulli distribution, but that individual's use risk varies, with sufficient population variability to match the anticipated extra-binomial variability noted from the prior study. Specifically a beta-binomial distribution is assumed for daily use with parameters (b1= .45, b2=1). Since the mean of the beta binomial is b1/b1+b2, then the expected number of use days in a 30 day period is 9.31 and the standard deviation is 9.08.

While verification of some daily reports will be substantiated with urine testing, underreporting of use may occur. We anticipate that this underreporting may vary among individuals. In the simulation underreporting of use is modeled under assumptions of complete accuracy (0% underreporting), 20% underreporting and 40% underreporting of use days. Conditional on use, the probability of underreporting is modeled with a beta-binomial distribution with parameters of (.2, .8) for the 20% level and (.4, .6) for the 40% level.

Losses to follow-up are assumed to occur in 5% of the participants prior to initiation of the evaluation period. In addition, a daily loss probability is presumed that is scaled by the individuals mean use probability from the initial beta-binomial distribution. Thus, individuals with higher use rates are more likely to discontinue. In the simulation, the unscaled daily probability is set at .008 and this results in an 18% dropout rate during the evaluation period.

The test statistic used in the simulation is a nonparametric test (Wilcoxon) comparing use-free days in the 2 active treatment arms using an experimentwise 5% Type 1 error from performing 2 pairwise tests of the buprenorphine arms versus control each at the 2.5% one-tailed level. In individuals who withdraw during the evaluation period, the score is the percentage of use-free days during the completed period scaled up for the entire 30-day observation period. Note that

the simulation utilized the number of use-free days as the endpoint, however, this analysis is comparable to one in which the endpoint is defined as number of use days.

Note that an alternative statistic, the t-test, was examined in the simulation but power was consistently less (and on the order of 20 percentage points less) for several key situations. Simulated power was also less when analyzing the main effect from a repeated measurement linear model.

Under these assumptions, the following results were obtained with the randomized sample size of 300 (i.e. 100/arm) and 1,000 replications of each condition.

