#### Simulated study pairwise power with N=100 randomized individuals per arm

Increased # of Non-Use Days With Treatment	Use 0%	Underreporting 20%	Percentage 40%
2.27	.635	.570	.515
3.16	.886	.873	.777
3.94	.974	.968	.915

Under these assumptions, an improvement of 3.16 days in the 30 day evaluation period can be reliably detected with >85% power if the underreporting percentage is bounded by 20%. When delta approaches 4, in excess of 90% power is available. Note that the standard errors for the first column results are .015, .010 and .005.

The above excludes the 5% of the randomized individuals who fail to enter the evaluation period. If one were to impute the maximally pessimistic situation (all treated use daily, all control use never) for these cases then simulated power is 77% for the difference of 3.94 days, no underreporting.

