#### **10.7** Missing Data and Dropouts

The primary analysis will be performed in the group of individuals who initiate the evaluation period. Minimal loss is anticipated between randomization and this time point given the short time period. Intent-to-treat analysis with all cases will be performed assuming both the maximally pessimistic situation (all treated use daily, all control use never) and baseline use levels for these early withdrawals. The primary endpoint score imputes dropouts during the evaluation period to have use rates equal to that observed through the period prior to dropout. The TES will be used as a secondary analysis to assist with evaluating this effect. Note that in the design simulations, the TES 12-day analysis was observed to be less powerful than the analysis of the selected primary endpoint. But design assumptions did not assume interactions with treatment for either underreporting or withdrawal events.

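### The 77% worst-case intent-to-treat power rests on 5% loss over days 1-24, which is out of line with the 18% assumed for days 25-54

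*Protocol*

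**What the plan says.** Section 10.2 gives two loss assumptions. For the time before the evaluation period: "Losses to follow-up are assumed to occur in 5% of the participants prior to initiation of the evaluation period". For the evaluation period itself, a daily loss probability is scaled by each person's use probability: "the unscaled daily probability is set at .008 and this results in an 18% dropout rate during the evaluation period". Section 10.1.2 places the evaluation period at days 25 to 54, so the first assumption covers 24 days and the second 30.

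The power table in Section 10.2 leaves out the early 5%. When these cases are instead imputed as daily use in every treated participant and no use in every control, "then simulated power is 77% for the difference of 3.94 days, no underreporting". Section 10.7 confines the primary analysis to those who start the evaluation period. It plans intent-to-treat analyses under two imputations, the worst case just described and baseline use levels. It supports the low early loss with one sentence: "Minimal loss is anticipated between randomization and this time point given the short time period".

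**The concern.** The two windows are of similar length, but the assumed daily loss in the second is about three times that in the first. The reason given, a short interval, cannot explain this: 24 days is 80% of 30 days.

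Everyone lost before day 25 is outside the primary analysis, so that analysis set is not the full randomised set. The worst-case intent-to-treat analysis is one of the safeguards, and 77% is the only power quoted for any intent-to-treat analysis. If that figure exists only because early loss was set at 5%, a reader will believe that the design withstands a check which it would fail at the dropout rate the section itself expects a few weeks later.

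**Working it through.** **Inputs (Section 10.2 unless stated).** Use model: "Specifically a beta-binomial distribution is assumed for daily use with parameters (b1= .45, b2=1". Tests: "performing 2 pairwise tests of the buprenorphine arms versus control each at the 2.5% one-tailed level", by Wilcoxon. Size: "the following results were obtained with the randomized sample size of 300 (i.e. 100/arm) and 1,000 replications of each condition". Dropouts in the evaluation period have their observed rate scaled to 30 days. Early window 24 days, evaluation window 30 days (Section 10.1.2).

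**1. Reproducing the plan's figures.**
- Mean use days: 30 × .45/1.45 = 9.31.
- Variance: 30 × .3103 × .6897 × (31.45/2.45) = 82.4, so SD 9.08. Both agree with "the expected number of use days in a 30 day period is 9.31 and the standard deviation is 9.08".
- The Protocol does not say how the treatment effect is generated. Subtracting c from each person's daily use probability (floor 0) lowers mean use by 30 × (c − c^1.45/1.45). For c = .10, .15, .20 this gives 2.27, 3.18 and 3.99 days, against 2.27, 3.16 and 3.94 in the table.
- With this form and loss following initial use, 3,000 replications put all nine table powers within 2 points (for example .895 against .886, and .856 against .873). Worst-case power at 3.94 days is .799, or .787 if loss follows use under treatment. The stated 77% has a simulation SE of √(.77 × .23/1000) = .013.

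**2. Daily loss implied by each assumption.**
- Days 1-24: 1 − .95^(1/24) = 0.21%.
- Days 25-54: 1 − .82^(1/30) = 0.66%. Ratio about 3.1.

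**3. Early loss at the section's own rate.**
- From the stated 18%: 1 − .82^(24/30) = 14.7%.
- From the .008, read as h = .008 × P/.3103 with P ~ Beta(.45, 1): 1 − E[(1 − h)^24] = 16.2%. This reading gives 19.5% over 30 days, or 15-17% if loss follows treated use; the stated 18% lies between.

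**4. Power when only early loss changes.** Each cell gives two values: loss following initial use; loss following use under treatment. There were 3,000 replications for the first row and 2,000 for the others.

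| Early loss | 3.16 days, no underreporting | 3.16 days, 20% underreporting | Worst case, 3.94 days |
|---|---|---|---|
| 5% | .895; .889 | .856; .830 | .799; .787 |
| 10% | .870; .869 | .830; .821 | .342; .327 |
| 14.7%, unrelated to use | .858; .848 | .816; .790 | .054; .051 |
| 16.2%, unrelated to use | .852; .846 | .809; .785 | .027; .027 |
| Use-scaled from day 1 | .922; .889 | .876; .842 | .062 (16.3% lost); .210 (12.9% lost) |

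A hand check on the printed powers, going from 95 to 84 entrants per arm with loss unrelated to use, multiplies the noncentrality by √(84/95) = .940. Then .886 becomes .845 and .873 becomes .830.

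**5. Why the worst case collapses.** At 3.94 days a treated participant does better than a control with probability about .66. If a fraction q of each arm is imputed against treatment, then, ignoring ties, this becomes (1 − q)² × .66: .596 at 5%, .535 at 10%, .480 at 14.7%, .463 at 16.2%. Ties bring the last to about .50, the value under no effect.

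**6. Other effect forms.**
- Half abstinence, half lower use risk: worst-case power .770, .318 and .070 at 5%, 10% and use-scaled loss. Evaluable power at 3.16 days goes from .872 to .83.
- Responder mixture: worst case .846, .406 and .030. Evaluable power goes from .918 to .851 under use-scaled loss.
- Random thinning: worst case .516, .119 and .002. This form misses the table badly (.699 against .886 at 3.16 days).

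The worst-case collapse appears in every form. The absence of any drop in evaluable power under use-scaled loss belongs to the form that reproduces the whole table.

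**The case against.** The two loss figures are separate, disclosed inputs for separate periods, and the printed powers follow from them. Early retention could really be better: participants have just passed induction, and the second injection falls in week 5, a natural exit point. That is possible, but the Protocol does not argue it and relies only on the length of the interval.

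The 16.2% depends on a reading of how the .008 is scaled. This stands as a caveat, which is why 14.7%, taken directly from the stated 18%, is shown beside it. Both lead to the same conclusion.

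The worst-case imputation is a deliberate extreme bound, and its power must fall as loss rises. Section 10.7 also plans an intent-to-treat analysis at baseline use levels, which keeps about .93 power at 3.94 days in the rebuilt simulation with early loss at the section's own rate. It adds the TES, which under Section 10.3 counts a missing urine screen as not negative. This stands, and it limits the point: the bound is fragile, but it is not the only protection.

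A reader might also infer that the claim of more than 85% power at 3.16 days fails. That is not established. Early losses are outside the power table, the drop is a few points if loss is unrelated to use, and under use-scaled loss the form that reproduces the table shows none.

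**Conclusion.** The loss assumptions in Section 10.2 do not fit together, and Section 10.7 does not justify the difference. The section's own rate implies about 15-16% early loss instead of 5%.

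The effect on evaluable-sample power at 3.16 days is small: about 3-5 points if early loss is non-informative, which may take the 20%-underreporting figure below 85%, and no drop under use-scaled loss with the effect form that fits the table. The effect on the quoted 77% is large: about one third at 10% early loss, and at the section's own rate single digits in most variants, with .21 the highest value found. The 77% therefore should not be read as a property of the design at its own dropout rate.

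Two stronger readings are not supported. This is not an arithmetic error, since the stated figures can be reproduced from the stated inputs. Nor does it show that the trial is too small or the primary result unprotected. All re-run powers rest on an inferred effect mechanism, because the Protocol does not state one.

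**What to change.** In Section 10.2, apply one loss process to days 1-54, or give a reason for a lower rate before day 25. Restate the worst-case power at 3.94 days and the evaluable-sample power at 3.16 days for early loss of 5%, 10% and about 15-16%, and say how the treatment effect is generated. Report the power of the baseline-use intent-to-treat analysis alongside. In Section 10.7, bring the sentence on minimal early loss into line with these figures.

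The cost is a re-run of an existing simulation, some edited text, and a less favourable stated worst-case power. Enrolment and the planned analyses stay as they are.
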